### **13.4 Duration of the Study**

Enrolled subjects will participate for up to 52 weeks, including up to 4 weeks for screening activities.

The overall duration of the entire study (screening, treatment, and follow-up for all subjects) is expected to be approximately 3.5 years.

### **13.5 Records Retention**

Records of drug disposition, CRFs, and reports of the clinical trial must be maintained by the investigator for a period of at least 2 years following the date on which the test article is approved by FDA for marketing for the purposes that were investigated in the study. If no application is to be filed or if the application is not approved for such indication, the records must be stored for 2 additional years and then returned to ZIOPHARM. No records will be destroyed, but will be indefinitely stored.

### **13.6 Institutional Review Board**

This protocol and the study informed consent form must be reviewed and approved by the Institutional Biosafety Committee (where applicable) and IRB/IEC prior to the start of the study, and a copy of the approval letter supplied to ZIOPHARM. During the course of the study, the investigator shall make timely and accurate reports to the IRB/IEC on study progress at intervals not exceeding one year, as well as satisfying any other local IRB/IEC reporting regulations. Copies of all reports to, and correspondence with, the IRB/IEC must be provided to ZIOPHARM. Further, within three months of the completion or early termination of the study, a final report should be made to the IRB/IEC and ZIOPHARM by the investigator.

All protocol revisions must originate with and be documented by ZIOPHARM. If the requested revision is an amendment, the investigator must sign it. The FDA will be notified of all revisions by ZIOPHARM. The investigator must submit the amendment to his/her IRB/IEC for review and approval prior to implementation. Documentation of approval signed by the chairperson or designee of the IRB/IEC must be sent to ZIOPHARM.

It is the investigator's obligation to maintain an IRB/IEC correspondence file and to make this available for review to ZIOPHARM representatives as part of the routine study monitoring process.

### **13.7 Confidentiality and HIPAA**

The written Informed Consent will explain that study data will be stored in a database, maintaining confidentiality in accordance with national data legislation. All data processed by ZIOPHARM, or its representatives, will be identified by subject number and study code.

The written Informed Consent will also explain that, for data verification purposes, authorized representatives of ZIOPHARM, a regulatory authority (FDA), and/or the IRB/IEC may require direct access to parts of the hospital or clinic records relevant to the study that include the subject's medical history.

The Informed Consent Form will be accompanied by or include a separate document incorporating US Health Insurance Portability and Accountability Act (HIPAA)-compliant wording by which the subjects authorize the use and disclosure of their Protected Health Information.

### **13.8 Informed Consent**

#### ***13.8.1 FDA Informed Consent Requirements***

The investigator or his/her staff will explain the nature of the study, its purpose and associated procedures, the expected duration, and the potential risks involved to the prospective subject prior to enrollment. The Informed Consent should also indicate that, by signature, the subject or, where appropriate, a legal guardian, permits access to relevant medical records by the Sponsor and by representatives of the US FDA. If a prospective subject does not understand English, an appropriate translation into his or her primary language must be made available. The investigator or designee will obtain written, informed, and witnessed consent. The individual will have ample time and opportunity to ask questions. He/she will be informed about the right to withdraw from the study at any time without any disadvantage and without having to provide a reason for this decision. Following the discussion regarding the study, the prospective subject will be asked if he/she is willing to sign and personally date a statement of informed consent. Only if the individual voluntarily agrees to sign the informed consent statement and has done so, may he/she enroll into the study. A copy of his/her signed and dated informed consent will be provided to each subject. The signed Informed Consent Form is to remain in the investigator's file.

The Informed Consent Form and any other written information provided to the subjects will be revised whenever important new information becomes available that may be relevant to the subject's consent, or if there is an amendment to the protocol that necessitates a change to the content of the subject's informed consent. The investigator will inform the subject of changes in a timely manner and will ask the subject to confirm continuation of his/her participation in the study by his/her signature on the revised Informed Consent Form (if applicable). Any written Informed Consent Form and written information must receive IRB/IEC approval/favorable opinion in advance of use.

#### ***13.8.2 Subject Informed Consent Form***

ZIOPHARM will provide a sample subject Informed Consent Form for modification, as appropriate, by the investigator.

## 16 APPENDICES

### 16.1 Eastern Oncology Performance Status

#### ECOG PERFORMANCE STATUS

Grade	Performance Status
0	Fully active, able to carry on all pre-disease performance without restriction.
1	Restricted in physically strenuous activity but ambulatory and able to carry out work of a light or sedentary nature, eg, light house work, office work.
2	Ambulatory and capable of all self-care but unable to carry out any work activities. Up and about more than 50% of waking hours.
3	Capable of only limited self-care, confined to bed or chair more than 50% of waking hours.
4	Completely disabled. Cannot carry on any self-care. Totally confined to bed or chair.
5	Dead.

## 16.2 Recommended Regimen for Antipyretic and/or Analgesic Prophylaxis

Recombinant adenoviral vectors have the potential to elicit potent cellular and humoral immune responses. While the mechanism responsible for these effects is poorly understood, transient low-grade fevers are common after systemic recombinant adenovirus vector administration and temperatures up to 104° F with chills and generalized malaise have been observed with treatment. Because low grade fever is very likely to occur, prophylaxis with acetaminophen is strongly recommended.

- While meta-analyses suggest that ibuprofen is a better anti-pyretic medication than acetaminophen, acetaminophen also prevents and or reduces a fever. Acetaminophen is available without a prescription in 325 mg or 500 mg tablets. One to two tablets every 4 hours should be used to eliminate fever. The maximum dose of acetaminophen in adults should not exceed 4 grams in a 24-hour period.
- Side effects are rare, but some people are allergic to the medication. Over doses may cause liver failure. Therefore, people with liver disease and chronic alcohol users should avoid this medication.
- Common brand names of acetaminophen are Aspirin Free Anacin®, Feverall®, Genapap®, Panadol®, Tempra®, and Tylenol®.

In general, a fever can be treated with acetaminophen. Alternating doses of ibuprofen with acetaminophen will also effectively control fever and prevent accidental overdose. If a fever occurs in spite of prophylactic medication or does not respond to usual doses of acetaminophen, then a combination of both acetaminophen and ibuprofen may be needed to stop the fever.

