### **4.1 Inclusion Criteria**

1. Female, age  $\geq$  18 years

2. Histologically-confirmed, locally advanced or metastatic adenocarcinoma of the breast, irrespective of hormone receptor or human epidermal growth factor receptor 2 (HER2) status (triple negative receptor status is permitted)

- a. Endocrine resistant hormone receptor-positive breast cancer subject who in the opinion of the physician requires chemotherapy is eligible
- b. Inflammatory breast cancer permitted with 2 injectable lesions
- c. Subjects who have received prior (neo) adjuvant chemotherapy, hormonal therapy or trastuzumab are eligible

3. Achievement of SD or PR after a minimum of 12 weeks of pre-study first-, second-, or third-line standard chemotherapy

NOTE: A prior therapy that is not completed due to toxicity will not be considered a line of therapy for eligibility determination.

4. Presence of at least 2 measurable lesions as assessed by RECIST v1.1 criteria: one lesion is to be injected with Ad-RTS-IL-12 and defined as a non-target lesion

5. Standard treatment interrupted, except if anti-HER2 therapy

6. All treatment-related or radiation-related toxicities resolved to Grade 1 or lower

7. Submission of copies of tumor measurements and scans taken a) prior to starting the pre-study standard chemotherapy and b) at the end of a minimum of 12 weeks of the pre-study chemotherapy

8. Life expectancy > 12 weeks at study entry

9. Eastern Cooperative Oncology Groups (ECOG) performance status of 0 to 1 (see [Appendix 16.1](#))

10. Adequate bone marrow function as assessed by the following:

- a. ANC  $\geq$  1500/ $\mu$ L (without use of growth factors within 7 days of screening)
- b. ALC  $>$  700/ $\mu$ L
- c. PLT  $\geq$  100,000/ $\mu$ L
- d. Hb  $\geq$  9 g/dL

11. Adequate liver function as assessed by the following:

- a. Serum bilirubin  $\leq$  1.5 mg/dL, except as follows
  - i. Patients with Gilbert's disease: serum bilirubin  $<$  5 mg/dL
- b. AST, ALT, and ALP  $\leq$  2.5  $\times$  ULN, except as follows
  - i. Patients with hepatic metastases: ALT and AST  $\leq$  5  $\times$  ULN
  - ii. Patients with hepatic and/or bone metastases: alkaline phosphatase  $\leq$  5  $\times$  ULN

12. Adequate renal function as assessed by the following:

- a. Serum creatinine  $\leq$  1.5 mg/dL OR

- b. creatinine clearance of  $\geq$  60 mL/min based on a 24-hour urine collection

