## 6 TREATMENT PLAN

### 6.1 Ad-RTS-hIL-12 Dosage and Administration Procedures

The 0.5 mL dose of Ad-RTS-hIL-12 [REDACTED] must be injected into the same lesion and should be delivered by multiple injections with a fine needle (no finer than 27 gauge) directly into each quadrant of the lesion. Attention must be paid to adequately infiltrate the circumference of the tumor margins. Should the tumor selected for injection not support the entire Ad-RTS-hIL-12 injection volume (approximately 0.5 cc), another tumor should be injected with the remaining volume to ensure that all subjects receive [REDACTED]

[REDACTED] If another tumor is not available, then the remaining volume should be injected into a draining, pathologic lymph node of the injected tumor if possible. Lesions displaying signs of localized infection should not be injected.

**Note:** In the event that Ad-RTS-hIL-12 injection is not performed, subject will not continue in the study. The reason why injection was not given will be documented and the subject will be withdrawn from the study.

Administration of prophylactic antipyretics is strongly recommended during the first week after Ad-RTS-hIL-12 injection (see [Section 6.9](#) and [Appendix 16.2](#)). See note in [Section 6.2](#) concerning importance of proper hydration during treatment with Ad-RTS-hIL-12 immunotherapy.

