#### **6.9 Prophylactic Antipyretic and/or Analgesic Administration**

The use of antipyretics and/or analgesics is allowed as a prophylactic measure. Antipyretics and/or analgesics can be used anytime during study treatment, as indicated and required for patient safety and must be recorded as concomitant medications. Please refer to exclusion criteria for acute clinically significant and/or chronic infections.

NOTE: Since fever and flu-like symptoms (e.g., fever, headache, chills, dehydration, etc.) are commonly experienced following adenoviral vector administration, it is highly recommended that subjects be treated with prophylactic, antipyretic and/or analgesic medication prior to Ad-RTS-hIL-12 injection and during the first week after injection.

Please refer to [Appendix 16.2](#) for the recommended regimen for the prophylactic administration of antipyretics and/or analgesics.

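### Appendix 16.2: the acetaminophen schedule and the 4 g daily maximum beside it cannot both be followed with two 500 mg tablets per dose, and the liver caution is not tied to the eligibility criteria

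*Protocol*

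**What the plan says.** Protocol Appendix 16.2 sets out the antipyretic and analgesic regimen. On the drug: "Because low grade fever is very likely to occur, prophylaxis with acetaminophen is strongly recommended". On the tablets: "Acetaminophen is available without a prescription in 325 mg or 500 mg tablets". On the schedule, with no distinction by strength: "One to two tablets every 4 hours should be used to eliminate fever". The sentence after that sets the limit: "The maximum dose of acetaminophen in adults should not exceed 4 grams in a 24-hour period". The next bullet warns that overdose may cause liver failure and continues: "Therefore, people with liver disease and chronic alcohol users should avoid this medication".

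The body of the protocol sends the reader to this appendix. Section 6.1 states: "Administration of prophylactic antipyretics is strongly recommended during the first week after Ad-RTS-hIL-12 injection", and Section 6.2 repeats it. Section 6.9 says that "it is highly recommended that subjects be treated with prophylactic, antipyretic and/or analgesic medication prior to Ad-RTS-hIL-12 injection" and for the first week afterwards. All three sections refer to Appendix 16.2 for the regimen. None of them names acetaminophen or mentions the liver.

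Inclusion criterion 11 in Section 4.1 limits AST, ALT and ALP to 2.5 x ULN in general. It makes an exception that begins "Patients with hepatic metastases: ALT and AST" and raises the limit for those two enzymes to 5 x ULN.

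**The concern.** Two adjacent sentences in Appendix 16.2 give instructions that conflict over part of their range. A site applying the upper end of the schedule with the larger of the two named tablets would exceed the maximum that the same bullet sets. The appendix itself links overdose to liver failure, so the conflict bears on subject safety.

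The second matter is a gap. The appendix strongly recommends a drug and tells people with liver disease to avoid it, but does not define liver disease. The trial knowingly enrols subjects with hepatic metastases and raised transaminases. An investigator treating such a subject cannot tell from the protocol whether the recommendation or the caution governs.

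**Working it through.** **Inputs, all from Appendix 16.2**
- Tablet strength: 325 mg or 500 mg
- Tablets per dose: 1 or 2
- Interval: 4 hours
- Stated maximum: 4 g = 4,000 mg in 24 hours

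The 4 g figure is a stated limit, not a derived one, so there is no calculation of the plan's to reproduce. The question is whether the schedule stays within the limit over its whole range.

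**Formula.** Doses in 24 hours = 24 / 4 = 6. Daily total = strength x tablets per dose x 6.

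| Strength | Tablets per dose | Daily total | Share of 4,000 mg |
|---|---|---|---|
| 325 mg | 1 | 325 x 1 x 6 = 1,950 mg | 48.7% |
| 325 mg | 2 | 325 x 2 x 6 = 3,900 mg | 97.5% |
| 500 mg | 1 | 500 x 1 x 6 = 3,000 mg | 75% |
| 500 mg | 2 | 500 x 2 x 6 = 6,000 mg | 150% |

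Only the last row exceeds the limit, by 6,000 - 4,000 = 2,000 mg. At 1,000 mg per dose the limit is reached after 4,000 / 1,000 = 4 of the 6 scheduled doses.

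**The liver caution, with the passages side by side**
- Appendix 16.2 recommends acetaminophen prophylaxis without naming a subgroup, then says in a later bullet that people with liver disease should avoid it.
- Sections 6.1, 6.2 and 6.9 recommend antipyretics and/or analgesics in general and refer to that appendix. They add no hepatic exception.
- Inclusion criterion 11 admits hepatic metastases with ALT and AST up to 5 x ULN.
- Exclusion criterion 18 in Section 4.2 removes chronic hepatitis B and C. No exclusion criterion addresses hepatic metastases.

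Taken together, the recommendation and the caution can be read as a rule with its exception. What is missing is a statement of whether the subjects admitted by criterion 11 fall within that exception.

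**The case against.** The strongest reply is that the cap follows the schedule at once, in the same bullet. A dose range followed by a daily maximum is ordinarily read as a range subject to that maximum, and three of the four combinations respect it. This stands: a reader might infer that the protocol permits 6 g a day, and the appendix read as a whole does not. It leaves the narrower point untouched, because a schedule stated for both strengths still cannot be followed at its upper end with one of them.

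A reader might also infer exposure at 6 g for the whole first week. The documents do not support that. The schedule sentence concerns eliminating fever, the first week comes from the general antipyretic recommendation, and no section prescribes maximum dosing around the clock for a week.

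On the liver, it is fair to say that Sections 6.1, 6.2 and 6.9 do not name acetaminophen and that they point to the appendix carrying the caution. Section 7.1 also permits NSAIDs, and the appendix discusses ibuprofen, so acetaminophen is not the only antipyretic the protocol contemplates. The inference that the protocol directs subjects with liver disease to take acetaminophen therefore fails. Treating hepatic metastases or raised transaminases as liver disease is itself an inference. What remains is that the protocol leaves the question open while enrolling these subjects.

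Finally, one might argue that acetaminophen injury would distort the primary safety endpoint or the toxicity boundary. That is speculative. Section 6.9 requires antipyretics to be recorded as concomitant medications, Section 10.5 requires the causality assessment to consider other drugs, and the boundary in Section 12.4.2 counts only related, treatment refractory Grade 3 or 4 events. No route to a wrong stopping decision can be shown from the text.

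**Conclusion.** The point holds in a limited form. In one of the four combinations that the schedule covers, the 24-hour total is 6.0 g against a stated 4 g, so two adjacent instructions are incompatible there. This rests on two readings: that the schedule applies to both named strengths, since the text does not separate them, and that dosing every 4 hours continues for 24 hours, which is the period over which the maximum is defined.

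The liver caution is a lesser matter: an undefined term whose relation to inclusion criterion 11 is not stated, rather than a direct contradiction.

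Both are patient-safety inconsistencies of wording in a recommended, non-mandatory regimen. Sample size, error rates, stopping boundaries and the analysis are unaffected.

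**What to change.** The sponsor's clinical team should make two changes of wording.

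1. In Appendix 16.2, reconcile tablet strength, tablets per dose and interval with the stated daily maximum, so that no combination the text permits exceeds it.
2. Reconcile the liver-disease caution with inclusion criterion 11 and with the prophylaxis recommendations in Sections 6.1, 6.2 and 6.9, so that a site can tell whether the caution applies to subjects with hepatic metastases or raised transaminases.

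The clinical content is for that team to decide; no dose or clinical rule is proposed here. The cost is an edit to one appendix and a cross-reference in Section 6, with no change to the visit schedule, sample size or analysis.

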### 16.3 RECIST v. 1.1

## 16.4 New York Heart Association Classification

### Classes of Heart Failure

Doctors usually classify patients' heart failure according to the severity of their symptoms. The table below describes the most commonly used classification system, the New York Heart Association (NYHA) Functional Classification. It places patients in one of four categories based on how much they are limited during physical activity.

Class	Functional Capacity: How a patient with cardiac disease feels during physical activity
I	Patients with cardiac disease but resulting in no limitation of physical activity. Ordinary physical activity does not cause undue fatigue, palpitation, dyspnea or anginal pain.
II	Patients with cardiac disease resulting in slight limitation of physical activity. They are comfortable at rest. Ordinary physical activity results in fatigue, palpitation, dyspnea or anginal pain.
III	Patients with cardiac disease resulting in marked limitation of physical activity. They are comfortable at rest. Less than ordinary activity causes fatigue, palpitation, dyspnea or anginal pain.
IV	Patients with cardiac disease resulting in inability to carry on any physical activity without discomfort. Symptoms of heart failure or the anginal syndrome may be present even at rest. If any physical activity is undertaken, discomfort increases.

Class	Objective Assessment
A	No objective evidence of cardiovascular disease. No symptoms and no limitation in ordinary physical activity.
B	Objective evidence of minimal cardiovascular disease. Mild symptoms and slight limitation during ordinary activity. Comfortable at rest.
C	Objective evidence of moderately severe cardiovascular disease. Marked limitation in activity due to symptoms, even during less-than-ordinary activity. Comfortable only at rest.
D	Objective evidence of severe cardiovascular disease. Severe limitations. Experiences symptoms even while at rest.

#### For Example:

- A patient with minimal or no symptoms but a large pressure gradient across the aortic valve or severe obstruction of the left main coronary artery is classified:
  - **Function Capacity I, Objective Assessment D**
- A patient with severe anginal syndrome but angiographically normal coronary arteries is classified:
  - **Functional Capacity IV, Objective Assessment A**

## 16.5 CTCAE v. 4.03

Please refer to the following website for the *Common Terminology Criteria for Adverse Events (CTCAE)*, Version 4.03, published June 14, 2010 by the National Cancer Institute:

[REDACTED]

**CONFIDENTIAL**

## Tabular Summary of Revisions Implemented in the Amended Protocol

Section in Amended Protocol	Revised or Deleted Text/Section	Rationale for Change
Title Page, Page Headings and Footers (page 1)	Specified “Original” for Date of Protocol (08 July 2014) and added Amendment 1, 05 November 2014.	To differentiate the original protocol from Amendment 1
Title Page, Page Headings and Footers (page 1)	Updated the primary contact for safety reporting from medical monitor to Safety Hotline Number.	SAEs should be reported by calling the Safety Hotline Number instead of the medical monitor
Protocol Synopsis (page 2)	In Research Hypothesis, specified standard therapy to be “chemotherapy” and changed anti-HER2 regimen to anti-HER 2 “antibody therapy” ; these changes were also made throughout the document.	Requested by principal investigator
Primary Objective and Primary Endpoints (pages 2, 8, 35, 73)	Primary Objective, changed from “To evaluate the safety and tolerability of one cycle of Ad-RTS-hIL-12 immunotherapy a) following a first- or second-line standard treatment in HER2-negative (HER2-) subjects, or b) together with a first- or second-line anti-HER2 treatment in HER2-positive (HER2+) subjects” to “To evaluate the safety and tolerability of one cycle of Ad-RTS-hIL-12 immunotherapy a) following a first- or second-line standard treatment in HER2-negative (HER2-) subjects, or b) together with a first- or second-line anti-HER2 antibody therapy in HER2-positive (HER2+) subjects as defined by Section 12.4.2 .	Requested by principal investigator and site staff
Secondary Objective and Primary Endpoints (pages 2, 8, 35, 73)	Secondary Objectives, deleted “To explore the biologic/immunologic effects of treatment on levels of the following cytokines in serum: interleukin-12 (IL-12), interleukin-10 (IL-10), and interferon-gamma (IFN- $\gamma$ )” and “To explore the effect of treatment on tumor infiltration by effector cells and immune suppressor elements” and replaced them with “To compare radiographic responses by irRC with conventional reporting by RECIST” and “To explore the impact of treatment on tumor and serum immune biomarkers”	Requested by principal investigator and site staff
Study Design (page 2 - 3)	Study Design language changed from “This is a single-arm pilot, single-center study to examine the safety, tolerability and preliminary efficacy of providing one cycle of Ad-RTS-hIL-12 immunotherapy following achievement of SD or PR on standard treatment as first- or second-line therapy in breast cancer subjects. The patient population will include patients with locally advanced or metastatic breast cancer of	Requested by principal investigator and site staff

Section in Amended Protocol	Revised or Deleted Text/Section	Rationale for Change
	
all subtypes. The safety of this therapy and the preliminary evidence of efficacy will guide further studies. Patients will be required to have SD or PR after completion of a minimum of 12 weeks on standard therapy. Subjects who have progressive disease (PD) or a CR after the standard therapy are not eligible for the study. Following entry into the trial, patients will go on a treatment holiday from the standard therapy and enter an immunotherapy phase of treatment” to “This is a single-arm, single-center study to examine the safety, tolerability and preliminary efficacy of one cycle of Ad-RTS-hIL-12 immunotherapy in women with advanced breast cancer and pre-study SD or PR after completion of a minimum 12 week course of standard first- or second-line chemotherapy. The patient population will include patients with locally advanced or metastatic breast cancer of all subtypes. The safety of this therapy and the preliminary evidence of efficacy will guide further studies. Subjects who have progressive disease (PD) or a CR after the standard therapy are not eligible for the study. Following entry into the trial, patients will go on a treatment holiday from chemotherapy and enter an immunotherapy phase of treatment. Continuation of HER2-targeted antibody therapy is permitted during this immunotherapy phase for women with HER2+ disease.”
	
Study Design (page 3)	Study Design language changed from “Radiographic PD at week 6 must be confirmed at least 4 weeks later.” To “Radiographic PD at week 6 must be confirmed at least 4 weeks later, either at week 12 or earlier if clinically necessitated. ”	Requested by principal investigator and site staff
Study Design (page 3)	Study Design language specified from standard therapy to “chemotherapy” and changed anti-HER2 therapy to anti-HER 2 “antibody therapy”	Requested by principal investigator and site staff
Pages 3, 6, 12, 36, 44, 46 and 54	“The first dose of veledimex followed 3 hours ± 30 minutes later by an intratumoral injection of Ad-RTS-hIL-12” to 3 hours ± 3 hours	Requested by principal investigator and site staff
Study Design (page 3)	Study Design, deleted “A post-treatment safety assessment visit will be conducted 28 days after the last dose of veledimex.”	Requested by principal investigator and site staff to lessen burden for patients
Study Design (pages 3 and 37)	Study Design, changed “The primary endpoint is safety/tolerability, defined as the proportion of patients who are able to complete 12 weeks on study without a Grade 3 or higher toxicity” to “The primary endpoint is safety/tolerability, defined as the	Requested by principal investigator and site staff

Section in Amended Protocol	Revised or Deleted Text/Section	Rationale for Change
	proportion of patients who are able to complete 12 weeks on study without Grade 3 or higher toxicity as defined by Section 12.4.2.	
Study Design (pages 3 and 37)	Study Design, changed “Additional secondary endpoints are the ORR, the DCR and the proportion of subjects who experience an improvement from a baseline tumor status from SD to PR/CR or from PR to CR, biologic/immunologic effects of treatment on levels of the cytokines in serum and the effect of treatment on tumor infiltration by immune cells. Biological markers of response (biomarkers) in serum will include various cytokines; for example, IL-12, IL-10 and interferon-gamma (IFN- $\gamma$ ). Additionally, immunocytochemistry will be performed on core or punch biopsy or fine needle aspiration (FNA) of the tumor and/or associated tumor-involved draining lymph nodes. Cellular infiltration by effector cells and immune suppressor elements will be evaluated using antibodies to various cluster of differentiation (CD) antigens, including CD3, CD4, CD8, CD25, FOX-P3, and CD56. In addition, blood for tumor markers such as CA 15-3 and CEA will be collected on day 1 and at 6 and 12 weeks after the start of immunotherapy” to “Additional secondary endpoints are the ORR, the DCR and the proportion of subjects who experience an improvement from a baseline tumor status from SD to PR/CR or from PR to CR. Disease responses by RECIST versus irRC will be explored. The effect of treatment on serum biomarkers [including IL-12, IL-10 and interferon-gamma (IFN-<math>\gamma</math>)] and tumoral immune cell subtypes (including CD8<math>^{+}</math> effector cells and T-regulatory cells) will also be explored.”	Requested by principal investigator and site staff
Exclusion Criteria (pages 5 and 39)	Exclusion #6 changed from “History of prior malignancy, unless the prior malignancy was diagnosed and definitively treated $\geq$ 5 years previously and showed no subsequent evidence of recurrence; adequately treated basal cell or squamous cell skin cancer or carcinoma in situ of the cervix, low grade thyroid are permitted to “An active, second potentially life-threatening cancer, adequately treated basal cell or squamous cell skin cancer or carcinoma in situ of the cervix, low grade thyroid are permitted.”	Requested by principal investigator and site staff
Safety Assessments (page 7)	Safety Assessments changed from “Subjects who experience drug-related Grade 3 AEs during the first 7 days of oral dosing with veledimex will interrupt further dosing. Subjects who experience drug-related Grade 4 AEs during the first 7 days of oral dosing with veledimex will discontinue therapy. The decision as to whether	Requested by principal investigator and site staff

Section in Amended Protocol	Revised or Deleted Text/Section	Rationale for Change
	subjects who experience severe or serious treatment-related adverse events will remain on study will be made by the investigator in conjunction with the Sponsor” to “Subjects who experience drug-related Grade 3 AEs during the first 7 days of oral dosing with veledimex will interrupt/discontinue further dosing at the discretion of the investigator . Subjects who experience drug-related Grade 4 AEs during the first 7 days of oral dosing with veledimex will discontinue therapy. The decision as to whether subjects who experience severe or serious treatment-related adverse events will remain on study will be made by the investigator in conjunction with the Sponsor Medical Monitor. ”	
Efficacy Assessments (page 7)	Efficacy Assessments changed from “Biologic/immunologic assessments will be performed using serum samples obtained at days 1, 3, 7, as well as tumor biopsies, preferably core biopsy (punch or FNA biopsy accepted in the absence of the core biopsy), taken on days 1 and 7 following initiation of immunotherapy” to “Biologic/immunologic assessments will be performed using serum samples obtained at screening, days 1, 3, 8, and weeks 6 and 12. Tumor biopsies will be obtained by interventional radiology prior to the intra-tumoral vector injection and again at 6 weeks. ”	Requested by principal investigator and site staff
Study Schema (page 10)	Updated Study Schema to match the Schedule of Study Procedures	Requested by principal investigator and site staff
Schedule of Study Procedures (page 11)	Updated Schedule of Study Procedures	Requested by principal investigator and site staff
Overall Study Design (page 36)	Overall Study Design, Changed from “This is a pilot single-arm, single-center study to examine the safety, tolerability and preliminary efficacy of providing one cycle of Ad-RTS-hIL-12 immunotherapy following achievement of SD or PR on standard treatment as first- or second-line therapy in breast cancer subjects” to “This is a single-arm, single-center phase 1b/II study to examine the safety, tolerability and preliminary efficacy of providing one cycle of Ad-RTS-hIL-12 immunotherapy following achievement of SD or PR on standard first- or second-line chemotherapy in breast cancer subjects.” Also changed, “Subjects who have PD or a CR after the standard therapy are not eligible for the study. Following entry into the trial, patients	Requested by principal investigator and site staff

Section in Amended Protocol	Revised or Deleted Text/Section	Rationale for Change
	will go on a treatment holiday from the standard therapy and enter an immunotherapy phase of treatment to “Subjects who have PD or a CR after the standard chemotherapy are not eligible for the study. Following entry into the trial, patients will go on a treatment holiday from the standard chemotherapy and enter an immunotherapy phase of treatment.”	
Overall Study Design (page 36)	Overall Study Design, changed from “For subjects with HER2- disease, the Ad-RTS-hIL-12 immunotherapy is intended to be given as a chemotherapy break, for example, to avoid intolerable or undesirable toxicity of the standard therapy. Ad-RTS-hIL-12 immunotherapy must be started within 4 weeks of stopping the pre-study standard therapy. Subjects with HER2+ disease will receive the Ad-RTS-hIL-12 immunotherapy in conjunction with first- or second-line anti-HER2 therapy, ie, subjects may continue anti-HER2-directed therapy during the study period” to “For subjects with HER2- disease, the Ad-RTS-hIL-12 immunotherapy is intended to be given as a chemotherapy holiday , for example, to avoid intolerable or undesirable toxicity of the standard therapy. Ad-RTS-hIL-12 immunotherapy must be started within 4 weeks of stopping the pre-study standard therapy. Subjects with HER2+ disease will receive the Ad-RTS-hIL-12 immunotherapy in conjunction with first- or second-line anti-HER2 antibody therapy, ie, subjects may continue anti-HER2-directed antibody therapy during the study period.”	Requested by principal investigator and site staff
Inclusion Criteria (pages 4 and 38)	Inclusion # 3, and 7, changed therapy to “ chemotherapy ”	Requested by principal investigator and site staff
Exclusion Criteria (page 5 and 41)	Exclusion #15, changed “International normalized ration (INR) and activated partial thromboplastin time (aPTT) $<1.5 \times \text{ULN}$ ” to “ International normalized ration (INR) and activated partial thromboplastin time (aPTT) <math>>1.5 \times \text{ULN}</math> ”	Requested by principal investigator and site staff
Section 5.4 (page 45)	Section 5.4, changed “Study drug container(s) with any remaining capsules should be returned to the study staff on Day 7” to “Study drug container(s) with any remaining capsules should be returned to the study staff on Day 8”	Requested by principal investigator and site staff
Section 6.1 (page 46)	Section 6.1, changed “If another tumor is not available, then the remaining volume should be injected into a draining, pathologic lymph node of the injected tumor” to “If another tumor is not available, then the remaining volume should be injected into a draining, pathologic lymph node of the injected tumor if possible ”	Requested by principal investigator and site staff

Section in Amended Protocol	Revised or Deleted Text/Section	Rationale for Change
Section 6.5 (page 47)	Section 6.5, changed “The decision as to whether subjects who experience severe or serious treatment-related adverse events will remain on study will be made by the investigator in conjunction with the Sponsor” to “The decision as to whether subjects who experience serious treatment-related adverse events will remain on study will be made by the investigator in conjunction with the Sponsor Medical Monitor ”	Requested by ZIOPHARM Safety and Medical Monitor for clarity
Section 6.7 (page 47)	Section 6.7, added “ Subjects who experience drug-related Grade 3 AEs during the first 7 days of oral dosing with veledimex will interrupt/discontinue further dosing at the discretion of the investigator. Subjects who experience drug-related Grade 4 AEs during the first 7 days of oral dosing with veledimex will discontinue therapy. The decision as to whether subjects who experience severe or serious treatment-related adverse events will remain on study will be made by the investigator in conjunction with the Sponsor Medical Monitor. ”	Requested by ZIOPHARM Medical Monitor for clarity
Section 7.1 (page 49)	Section 7.1, added “ HER-directed therapies in patients with HER2+ disease ”	Requested by principal investigator and site staff
Section 7.2 (page 49)	Section 7.2 changed “Any other investigational agent or anticancer therapy (chemotherapy, radiotherapy, etc) while receiving study treatment” to “Any other investigational agent or anticancer therapy (chemotherapy, radiotherapy, including corticosteroids , etc) while receiving study treatment”	Requested by ZIOPHARM Medical Monitor for clarity
Section 8.3.1.5 (page 51)	Section 8.3.1.5, changed “Females of childbearing potential will have a serum pregnancy test at the screening visit and a urine or serum pregnancy test on Day 1” to “Females of childbearing potential will have a serum pregnancy test at the screening visit within 14 days of dosing and a urine pregnancy test at Day 1. ”	Requested by principal investigator and site staff
Pages 58 - 65	Pages 58-65, updated assessments and visits to reflect the Schedule of Study Procedures	Requested by principal investigator and site staff
Section 9.2.1 (page 60)	Section 9.2.1, changed “In the current study, the baseline measurement will be based on the scans and measurements taken at the end of the pre-study standard therapy, as submitted by the investigator” to “In the current study, the baseline measurement will be based on the scans and measurements taken at the end of the pre-study standard	Requested by principal investigator and site staff

Section in Amended Protocol	Revised or Deleted Text/Section	Rationale for Change
	chemotherapy , as submitted by the investigator”	
Section 10.1 (page 65)	Section 10.1, changed “Any untoward medical occurrence in a patient or clinical investigation subject administered a pharmaceutical product that does not necessarily have a causal relationship the treatment” to “Any untoward medical occurrence in a patient or clinical investigation subject administered a pharmaceutical product that does not necessarily have a causal relationship to the treatment”	Grammatical Correction
